Investigational Product  Malfunction	Is defined as a preventative (vaccine), a therapeutic (drug or biologic), device, diagnostic, or palliative used as a test or control product in a clinical trial, including a product with a marketing authorization when used or assembled (formulated or packaged) in a way different from the authorized form, or when used for an unauthorized indication, or when used to gain further information about the authorized form.  Failure of a medical device to meet its performance
TVILLITATION OF	specifications or otherwise perform as intended. Performance specifications include all claims made in the labeling of the device. The intended performance of the device refers to the intended use for which the device is labeled or marketed.
Non-serious Adverse Event	Adverse event that does not meet the criteria for a serious adverse event.
Postmarketing/Post- authorization study	Any study conducted within the conditions laid down in product labelling and other conditions laid down for the marketing of the product or under normal conditions of use. A postmarketing study falls either within the definitions of an interventional or a non- interventional study and may also fall within the definition of a post-approval study.
Product Complaints	Any oral, electronic, or written communication that alleges deficiencies related to the identity (labeling), quality, durability, reliability, safety, effectiveness, or performance of a marketed product, including failure of the product, labeling or packaging to meet specifications, whether or not the product is related to or caused the alleged deficiency. A complaint may allege that an adverse event or medical device malfunction has occurred.
Randomized Subjects	Any subject who is assigned a randomized treatment.
Serious Adverse Device Effect (SADE)	Adverse device effect that has resulted in any of the consequences characteristic of a serious adverse event.
Serious Adverse Event (SAE)	
 
Adverse event that led to any of the following:
 
Death.
 
A serious deterioration in the health of the subject that either resulted in:
 

TDOC-0055656

Effective

2.0; Most-Recent; Effective; CURRENT

Page **9** of **59** 

	a. a life-threatening illness or injury.  Note: Life-threatening means that the individual was at immediate risk of death from the event as it occurred, ie, it does not include an event which hypothetically might have caused death had it occurred in a more severe form.
	b. any potentially sight-threatening event or permanent impairment to a body structure or a body function.
	c. in-patient hospitalization or prolonged hospitalization.  Note: Planned hospitalization for a preexisting condition, without serious deterioration in health, is not considered a serious adverse event. In general, hospitalization signifies that the individual remained at the hospital or emergency ward for observation and/or treatment (usually involving an overnight stay) that would not have been appropriate in the physician's office or an out-patient setting. Complications that occur during hospitalization are adverse events. If a complication prolongs hospitalization or fulfills any other serious criteria, the event is serious. When in doubt as to whether "hospitalization" occurred, the event should be considered serious.
	

d. a medical or surgical intervention to prevent

a) or b).

	
 
e. any indirect harm as a consequence of incorrect diagnostic test results when used within manufacturer's instructions for use.
 

	• Fetal distress, fetal death, or a congenital abnormality or birth defect.
	Refer to Section 11 for additional SAEs.
Serious Public Health Threat	Any event type which results in imminent risk of death, serious deterioration in state of health, or serious illness that requires prompt remedial action. This would include: events that are of significant and unexpected nature such that they become alarming as a potential public health hazard, eg, human immunodeficiency virus (HIV) or Bird Flu.

TDOC-0055656 Effective

Page 10 of 59

Significant Non-Serious Adverse Event	Is a symptomatic, device-related, non-sight threatening adverse event that warrants discontinuation of any contact lens wear for greater than or equal to 2 weeks.
	Refer to Section 11 for additional Significant Non-Serious AEs.
Unanticipated Serious Adverse Device Effect (USADE)	Serious adverse device effect which by its nature, incidence, severity or outcome has not been identified in the risk management file.
Use Error	Act or omission of an act that results in a different medical device response than intended by manufacturer or expected by user. Note: This definition includes slips, lapses, and mistakes. An unexpected physiological response of the subject does not in itself constitute a use error.

## 2 LIST OF ACRONYMS AND ABBREVIATIONS

## Table 2–1 List of Acronyms and Abbreviations Used in This Protocol

Abbreviation	Definition
ADD	Addition
ADE	Adverse device effect
AE	Adverse event
AOHG MF	AIR OPTIX plus HydraGlyde Multifocal contact lenses
BCVA	Best corrected visual acuity
CFR	Code of Federal Regulations
CL	Contact lens
cm	Centimeter
COL	Clinical Operations Lead
CRF	Case report form
CSM	Clinical Site Manager
D	Diopter(s)
DACP MF	DAILIES AquaComfort Plus Multifocal contact lenses
DT1 MF	DAILIES TOTAL1 Multifocal contact lenses
eCRF	Electronic case report form
EDC	Electronic data capture
FAS	Full analysis set
FDA	US Food and Drug Administration
GCP	Good Clinical Practice
HIV	Human immunodeficiency virus
ICF	Informed consent form
ICH	International Council for Harmonization of Technical Requirements
	for Pharmaceuticals for Human Use
IEC	Independent ethics committee
IP	Investigational product
IRB	Institutional review board
IRT	Interactive response technology
ISO	International Organization for Standardization
logMAR	Logarithm of the minimum angle of resolution
m	Meter
MF	Multifocal
mm	Millimeter

[figure not shown]
Page 12 of 59

Abbreviation	Definition	
MOP	Manual of procedures	
n	Number	
N/A	Not applicable	
NI	Noninferiority	
OD	Right eye	
OS	Left eye	
OU	Both eyes	
PAL	Progressive addition lens spectacles	
PP	Per protocol analysis set	
SAE	Serious adverse event	
SADE	Serious adverse device effect	
SD	Standard deviation	
US	United States	
USADE	Unanticipated serious adverse device effect	
VA	Visual acuity	

# **3 PROTOCOL SUMMARY**

[figure not shown]
Investigational product type	Device			
Study type	Interventional			
Investigational products	
 
Test Products:
 
AIR OPTIX plus HydraGlyde (lotrafilcon B) Multifocal (AOHG MF) contact lenses
 
DAILIES TOTAL1 (delefilcon A) Multifocal (DT1 MF) contact lenses
 
DAILIES AquaComfort Plus (nelfilcon A) Multifocal (DACP MF) contact lenses
 
Control Product:
 
			
Durmasa and	Progressive addition lens spectacles (PALs)  The purpose of this trial is to demonstrate a prinferiority in			
Purpose and rationale	The purpose of this trial is to demonstrate noninferiority in functional visual performance of Alcon's Precision Profile MF contact lenses compared to PALs in a presbyopic population.			
Objective(s)	The overall objective is to demonstrate noninferiority of multifocal (MF) contact lenses versus PALs in the transition time  The primary objective is to demonstrate noninferiority in transition time between distance and intermediate vision with MF contact lenses compared to PALs.			
Endpoint(s)	Primary effectiveness endpoint:  • Average transition time during alternate distance (4 m) and			
	intermediate (80 cm) viewing			

Page 14 of 59

TDOC-0055656 Effective

Page 15 of 59

Effective

Page 16 of 59

G 4 1 D ·	This is a new restriction of the second of t
Study Design	This is a prospective, randomized, parallel group study measuring the average transition time during alternate distance (4 m) and intermediate (80 cm) viewing
	intermediate (80 cm) viewing.
	Habitual contact lens wearers will be randomized to either AOHG MF, DACP MF, or DT1 MF contact lenses. This will be a double-masked trial for the contact lens group. PAL wearers will not be masked.
	Subjects will be expected to attend 1 or 2 office visits (Visit 2 may be performed on the same day immediately following Visit 1). All study contact lenses will be dispensed according to the subject's prescription and fitted using the Alcon MF fitting guide. PAL wearers will wear their habitual spectacles.
Subject population	Presbyopic subjects aged $\geq 38$ and $\leq 58$ years with normal eyes (other than correction for refractive error), whose habitual correction is either any MF contact lens (with a preference for Alcon Precision Profile Design wearers) with a LO or MED ADD (or equivalent to an ADD of max +2.00 D) or progressive addition lens spectacles. Wear of habitual correction must be at least 5 days per week and at least 6 hours per day.
	Planned number of subjects enrolled: ~ 60
	Required number of completed subjects: 48 (12 per group)
Key inclusion	Presbyopic subjects aged $\geq 38$ and $\leq 58$ years with normal eyes
criteria	(other than correction for refractive error), whose habitual
(See Section 8.1 for a	correction is either any MF contact lens (with a preference for
complete list of	Alcon Precision Profile Design wearers) with a LO or MED ADD
inclusion criteria)	(or equivalent to an ADD of max +2.00 D) or progressive addition
	lens spectacles. Wear of habitual correction must be at least 5 days
	per week and at least 6 hours per day.
Key exclusion	Monocular subjects or subjects fit with only one contact lens.
criteria	Known pregnancy or lactating. History of or planned refractive
(See Section 8.2 for a	surgery or irregular cornea in either eye.
complete list of	
exclusion criteria)	
· 	

TDOC-0055656 Effective

Page 17 of 59

Data analysis and	Planned Analysis	Planned Analysis			
sample size justification	To address the primary effectiveness objective, planned analysi summarized below:				analysis is
	Endpoint	Comparison	Statistica	al Method	
	Primary				
	Average transition time between distance and intermediate	MF lenses vs PALs		ized linear in = 0.5 se	
	No inferential testin	ng will be perfor	med for th	e safety aı	nalyses.
	Sample Size Justification				
Sample size calculation for the primary effectiveness expression (one-sided $\alpha = 0.05$ ) is summarized below:					dpoint
	Primary Endpoint	Assumptions		Power	N/group
	Average transition time between distance and intermediate	Common SD  NI margin =		80%	12
Key words	Presbyopic, multifocal				
Associated materials	Lubrication/re-wetting drops will not be permitted within 2 hours prior to study Visit 2.				

Page 18 of 59

Table 3–1 Schedule of Study Procedures and Assessments

	ALL SUBJECTS	MULTIFOCAL CONTACT LENS WEARERS	PROGRESSIVE ADDITION LENS SPECTACLE WEARERS	ALL SUBJECTS
Visit	Visit 1/	Visit 2/	Visit 2/	Unscheduled
Procedure/Assessment	Day 1 (May be performed same day as Visit 2)	Exposure/Exit  0-14 Days from Visit 1	Exposure/Exit  0-14 Days from  Visit 1	Visit
Informed Consent	✓			
Demographics	✓			
Medical History	✓	✓	✓	✓
Concomitant Medications	✓	✓	√	√
Inclusion/Exclusion	✓	✓	√	
Randomize		✓		
Habitual correction (type/brand, power)		√	✓	
Dispense study contact lenses in a masked manner		✓		

TDOC-0055656 Effective

Page 19 of 59

	ALL SUBJECTS	MULTIFOCAL CONTACT LENS WEARERS	PROGRESSIVE ADDITION LENS SPECTACLE WEARERS	ALL SUBJECTS
Visit	Visit 1/ Screening	Visit 2/ Exposure/Exit	Visit 2/ Exposure/Exit	Unscheduled Visit
Procedure/Assessment	Day 1 (May be performed same day as Visit 2)	0-14 Days from Visit 1	0-14 Days from Visit 1	
		✓		
Transition time during alternate distance (4 m) and intermediate (80 cm) viewing		√	√	

TDOC-0055656 2.0; Most-Recent; Effective; CURRENT Effective

Page 20 of 59

	ALL SUBJECTS	MULTIFOCAL CONTACT LENS WEARERS	PROGRESSIVE ADDITION LENS SPECTACLE WEARERS	ALL SUBJECTS
Visit	Visit 1/	Visit 2/	Visit 2/	Unscheduled
VISIT	Screening	Exposure/Exit	Exposure/Exit	Visit
Procedure/Assessment	Day 1 (May be performed same day as Visit 2)	0-14 Days from Visit 1	0-14 Days from Visit 1	
AEs	✓	√	√	✓
Device deficiencies	✓	✓		(✓)
Exit form†	(✓)	√	✓	(✓)

(✓) assessment performed as necessary, eg, decrease of VA by 2 lines or more with investigational product (IP) \*source only; † must be performed as a screening assessment and prior to study exit

#### 4 PROTOCOL AMENDMENTS

[figure not shown]
Modification of the protocol is prohibited without prior written agreement in the form of a protocol amendment. All amendments must be created by the Study Sponsor and must be approved by the IRB/IEC and global and regional Health Authorities, as applicable, prior to implementation except when required to mitigate immediate safety risks or when the changes involve only logistical or administrative revisions.

2.0; Most-Recent; Effective; CURRENT

Page 21 of 59

[figure not shown]
Amendments may necessitate that the informed consent and other study-related material be revised. If the consent form is revised, all subjects currently enrolled in the study must sign the approved, revised informed consent (re-consent), as required by the IRB/IEC.

### 4.1 Amendments

TDOC-0055656 2.0; Most-Recent; Effective; CURRENT Effective

Page 22 of 59

[figure not shown]

TDOC-0055656 2.0; Most-Recent; Effective; CURRENT Effective

[figure not shown]
Page 23 of 59

Changes made to align with the MOP

Page 24 of 59

[figure not shown]

TDOC-0055656 Page 25 of 59 Effective

TDOC-0055656 2.0; Most-Recent; Effective; CURRENT

Page 26 of 59

#### 5 INTRODUCTION

#### 5.1 Rationale and Background

Presbyopia is an age-related vision condition in which the crystalline lens gradually loses its ability to change shape when acted upon by the ciliary muscle. It typically becomes evident by 40 to 45 years of age and it is expressed by a reduction in the ability to define letters or objects at near distance. The condition can be corrected by the use of single-vision or bifocal spectacles, PALs, or MF contact lenses.

[figure not shown]
Alcon manufactures three MF contact lenses (lotrafilcon B, nelfilcon A, and delefilcon A) with the same Precision Profile optical design that allows for the same fitting process with all three lenses. The AOHG MF soft contact lenses are made of a lens material that is approximately 33% water and 67% lotrafilcon B, a fluoro-silicone containing hydrogel which is surface-treated. These lenses may be prescribed for daily wear or extended wear for up to 6 nights of continuous wear with removal for disposal, or cleaning and disinfection prior to reinsertion, as recommended by the eye care professional.

The DACP MF daily disposable, soft contact lens is made up of 69% water and 31% nelfilcon A polymer (polyvinyl alcohol partially acetalized with N-formylmethyl acrylamide). DT1 MF (delefilcon A) daily disposable, soft contact lenses feature a unique water gradient composition from a silicone-rich highly breathable core (33% water) to an ultrasoft hydrophilic surface gel (> 80% water at the lens surface).

The goal of this study is to demonstrate seamless transition vision in presbyopes using Precision Profile Design MF contact lenses.

Page 27 of 59

## **5.2** Purpose of the Study

At the end of the study, a clinical study report will be prepared in accordance with applicable regulatory requirements and standards.

#### 5.3 Risks and Benefits

A summary of the known and potential risks and benefits associated with AOHG MF, DACP MF, and DT1 MF contact lenses can be found in their respective package inserts. Safety information about AOHG MF, DACP MF, and DT1 MF contact lenses may be found in their respective product labeling.

There may also be unknown risks to use of AOHG MF contact lenses, DT1 MF contact lenses, or DACP MF contact lenses. Any risk to subjects in this clinical study will be minimized by compliance with the eligibility criteria and study procedures, clinical oversight, and monitoring. In this study, the duration of the planned clinical exposure of the currently marketed MF contact lenses is up to 3 hours. Site personnel will educate subjects on proper hygiene and lens care, handling, and compliance with use of the study contact lenses, as applicable. Site personnel will advise the subjects to remove contact lenses and/or alert site staff for prompt follow-up if there are symptoms such as ocular discomfort, foreign body sensation, excessive tearing, vision changes, or hyperemia.

Refer to the product label for additional information.

#### 6 STUDY OBJECTIVES

## 6.1 Primary Objective(s)

Objective(s)	Endpoint(s)

[figure not shown]
Page 28 of 59

The primary objective is to demonstrate noninferiority in transition time between distance and intermediate vision with MF contact lenses compared to PALs.

Average transition time during alternate distance (4 m) and intermediate (80 cm) viewing

## 6.2 Secondary Objective(s)

Not Applicable.

TDOC-0055656 2.0; Most-Recent; Effective; CURRENT Effective

Page 29 of 59

## 6.4 Safety Objective(s)

Table 6–3 Safety Objective(s)

Objective(s)	Endpoint(s)
Demonstrate the safety profile of the study products.	
 
Adverse events (Any AEs and device deficiencies for non-study marketed devices/products will be considered and processed as spontaneous (following the post-market vigilance procedures) and should be communicated to the device's/product's manufacturer as per local requirements.)
 
Biomicroscopy findings
 
Device deficiencies
 

#### 7 INVESTIGATIONAL PLAN

## 7.1 Study Design

This is a prospective, randomized parallel group study measuring the average transition time

[figure not shown]
Habitual contact lens wearers will be randomized to either AOHG MF, DACP MF, or DT1 MF contact lenses. This will be a double-masked trial for the contact lens group. The PAL wearers will not be randomized and will wear their habitual PALs during the study. This group will not be masked. Investigators will be masked to the brand and type of PAL for habitual PAL wearers.

2.0; Most-Recent; Effective; CURRENT
Page 30 of 59

Subjects will be expected to attend 1 to 2 office visits (Visit 2 may be performed on the same day immediately following Visit 1). All study contact lenses will be prescribed according to the subject's prescription and fitted using the Alcon MF fitting guide. PAL wearers will wear their habitual spectacles. Subjects are expected to complete the study in approximately 2 to 3 hours.

The study is expected to be completed in approximately 8 weeks.

Figure 7-1 Study Design

## 7.2 Rationale for Study Design

In this study, the visual performance of the current marketed AOHG MF, DACP MF, and DT1 MF contact lenses will be assessed in a prospective, double-masked (for the contact lens group) design with up to 3 hours of exposure to the study lenses. The MF contact lens performance will be compared to the visual performance of PAL. The study design and the exposure duration of the study lenses is supported by the MF fitting guidelines for the Precision Profile Design contact lenses.

## 7.3 Rationale for Duration of Treatment/Follow-Up

The duration of exposure to the contact lenses was chosen to address the objective of this study, and is aligned with MF fitting guidelines for initial fit assessment following lens insertion.

#### 7.4 Rationale for Choice of Control Product

PALs were chosen as the control product to address the study objectives. PALs are an alternative to MF contact lenses for the correction of presbyopia.

## 7.5 Data Monitoring Committee

Not applicable.

#### 8 STUDY POPULATION

The study population consists of male or female subjects aged  $\geq 38$  and  $\leq 58$  with presbyopia. The aim is to enroll approximately 60 subjects at approximately 2 sites; 1 in the United Kingdom and 1 in the United States (US), with a target of 48 total subjects completed. Each site is expected to enroll approximately 30 subjects with a target of 24 completed (approximately 6 subjects per group at each site). Site-specific targets may vary based upon individual site capabilities. Estimated time needed to recruit subjects for the study is approximately 6 to 8 weeks. Because a 20% screening failure and/or discontinuation rate is expected, approximately 60 subjects are expected to be enrolled.

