# 9.3 Treatment Assignment / Randomization

Habitual contact lens wearing subjects will be randomized in a 1:1:1 ratio to receive AOHG MF, DT1 MF, or DACP MF, respectively. Habitual PALs wearing subjects will not be randomized.

Only after signing the ICF, a subject will be assigned a subject number by the electronic data capture system.

A randomization list will be generated using a validated system that automates the random assignment of treatment arms to randomization numbers in the specified ratio. Subjects will be assigned treatment according to the randomization list uploaded in the IRT system. The randomization list will be generated and maintained by the Study Sponsor.

At Visit 2, all eligible subjects in the contact lens group will be randomized via the EDC/IRT integration system to one of the treatment arms. The unmasked study coordinator will access the respective system after confirming that the subject meets all the eligibility criteria. A randomization number will be automatically assigned to the subject according to the subject randomization list but will not be communicated to the site user. The EDC/IRT integration system will inform the site user of the treatment assignment to be dispensed to the subject.

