## 12.4 Effectiveness Analyses

This study	defines 1 primary,			
	All effectiveness evaluations will use the FAS as the primary analysis set.			
	analyses of the primary	will be		
conducted using the PP Analysis Set only if the number of subjects excluded from the PP				
Analysis S	Set exceeds 5% of the FAS.			

A sequential gatekeeping strategy will be used to control testing of multiple effectiveness endpoints. Therefore, the overall Type I error will be maintained at one-sided 0.05 with the following testing order:

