## 12.8 Sample Size Justification

Sample size calculation is based on published results regarding response time for distance and near visual acuity, with high and low contrast.

To demonstrate noninferiority (margin = 0.5 seconds) as a one-tailed hypothesis with  $\alpha = 0.05$ , and using a common standard deviation of 0.456, 80% power can be attained with a sample size of 48 (12 per group). For a comparison using a 3:1 ratio, required sample sizes for 80% power are 24:8 (test:control).

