## 7 Sample Size and Power Calculations

Sample size calculation is based on published results regarding response time for distance and near visual acuity, with high and low contrast.

To demonstrate noninferiority (margin = 0.5 seconds) as a one-tailed hypothesis with  $\alpha = 0.05$ , and using a common standard deviation of 0.456, 80% power can be attained with a sample size of 48 (12 per group). For a comparison using a 3:1 ratio, required sample sizes for 80% power are 24:8 (test:control).

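### The balance of spectacle and lens wearers between the two sites is only a soft target, and the visible primary model has no site term to protect the non-randomised MF minus PAL contrast

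*Protocol*

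**What the plan says.** Protocol section 8 plans two sites, one in the UK and one in the US. Each should complete 24 subjects, which it breaks down as "approximately 6 subjects per group at each site". With three lens groups and one spectacle group, that means 18 MF and 6 PAL per site. The next sentence reads: "Site-specific targets may vary based upon individual site capabilities". It gives no limit, and no visible text sets a floor, cap or quota by cohort and site.

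Randomisation is 1:1:1 among the three MF lenses only. On the control group, Protocol 9.3 says: "Habitual PALs wearing subjects will not be randomized". SAP 1.3 agrees.

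The primary comparison pools the three MF groups against PAL. Protocol 12.4.1.2 specifies a generalized linear model with a four-level treatment term. SAP 4.3.1 specifies a mixed model whose only fixed effect is lens, plus within-subject correlation. Neither has site. Protocol 12.4 states that "the overall Type I error will be maintained at one-sided 0.05".

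**The concern.** The randomisation does not protect the contrast that decides the study. It balances the MF lenses against each other, and they are then pooled. The share of each cohort at each site is set by recruitment, and habitual MF wearers and PAL wearers need not be equally easy to find at both places.

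The endpoint is a timed task, and procedures are delegated to site personnel, so a difference in recorded times between sites is plausible. The documents give no estimate of it. With no site term, any such difference is carried into MF minus PAL whenever the cohort mix differs by site. Depending on direction, the result is a false noninferiority claim or a missed true one.

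**Working it through.** **Inputs.** Margin 0.5 s and one-sided alpha 0.05 (Protocol 12.8), "using a common standard deviation of 0.456" (SAP 7), and 48 completers as 36 MF and 12 PAL. Assumed here, because the documents do not give them: a true difference of 0 for power, one averaged value per subject, an additive site effect of 0.2 or 0.3 s, and the drifted splits below. Sites are labelled A and B.

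**1. The plan's own sample size.** With the noncentral t distribution, 11 per group gives 79.9% power and 12 per group gives 83.1%. At 3:1, 21:7 gives 78.9% and 24:8 gives 83.6%. The stated 12 per group and 24:8 are therefore reproduced. At 36:12, SE = 0.456 × √(1/36 + 1/12) = 0.152 s, and power is 94.5%.

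**2. Bias without a site term.** Bias = (MF share at A − PAL share at A) × (site A effect − site B effect).

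- Planned split, PAL 6:6 and MF 18:18: (18/36 − 6/12) = 0, so the bias is 0 for any site effect.
- Illustrative drift, PAL 10:2 and MF 14:22, still 24 completers per site: 14/36 − 10/12 = −0.444. At 0.2 s the bias is 0.089 s. At 0.3 s it is 0.133 s, which is 27% of the margin.

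**3. Consequences at PAL 10:2, MF 14:22.** Holding SE at 0.152:

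| Assumed site effect | Type I error if bias favours MF | Type I error if bias favours PAL | Power if bias favours PAL |
|---|---|---|---|
| 0.2 s | 14.3% | 1.3% | 85% |
| 0.3 s | 21.7% | 0.6% | 77% |

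The omitted site effect also adds to the residual variance. The average within-group site variance is (12 × 10×2/12² + 36 × 14×22/36²)/48 = 0.213 times the squared site effect. At 0.3 s the SD becomes √(0.456² + 0.213 × 0.3²) = 0.477. Simulating the split with this included gives type I errors of 13.5% and 19.5%, and power of about 84% and 74%.

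**4. What a site term costs.** With treatment and site in the model, SE = 0.456/√W, where W is the sum over sites of (PAL × MF)/(PAL + MF).

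| PAL A:B | MF A:B | W | SE | Variance ratio | Power |
|---|---|---|---|---|---|
| 6:6 | 18:18 | 4.5 + 4.5 = 9 | 0.152 | 1.00 | 94.5% |
| 10:2 | 14:22 | 5.83 + 1.83 = 7.67 | 0.165 | 1.17 | 91.1% |
| 12:0 | 12:24 | 6 + 0 = 6 | 0.186 | 1.50 | 84.1% |
| 12:0 | 6:30 | 4 + 0 = 4 | 0.228 | 2.25 | 69.7% |
| 12:0 | 0:36 | 0 | – | – | not estimable |

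The first three rows have 24 completers at each site. The last two need site totals of 18 and 30, and of 12 and 36.

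**The case against.** The plan does set a balance: the target of about six per group at each site is exactly 3:1. The sentence that follows ties variation to site capability and can be read as referring to site totals, not to the mix of cohorts. A reader might infer that nothing holds the ratio. That goes too far, because there is a target; what is missing is any means of enforcing it.

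A reader might also infer that the primary result could become largely a UK-versus-US comparison. With 24 completers per site and 12 PAL subjects in total, the difference in site share cannot exceed 1 − 12/36 = 0.67. Complete separation needs site totals of 12 and 36, far from the plan.

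A third tempting reading is that analysis cannot repair a site with almost no PAL subjects. The table above shows otherwise. If site effects are additive, a site term works in every split short of complete separation, although with no PAL subjects at one site the comparison rests on the other site alone.

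The site effect itself is assumed. Fixed viewing distances, voice-recorded readings and a manual of procedures that is not available here all point towards standardisation. If the bias favours PAL, the false-positive rate falls to about 1%, and the cost is lost power. SAP 4.5, on subgroups and baseline factors, is listed in the contents but its text is not visible, so a site summary there cannot be ruled out.

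These points limit the size and likelihood of the harm. They do not supply a site term in the visible primary model or make the target binding.

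**Conclusion.** The concern holds as a conditional risk: an unenforced balance combined with an unadjusted, non-randomised contrast. At the planned split there is no bias from site. At PAL 10:2 and MF 14:22 with a 0.2 to 0.3 s site effect, the bias is 0.09 to 0.13 s. The type I error is then about 13 to 20% if the bias favours MF (14 to 22% if the extra residual variance is ignored). If it favours PAL, power is about 77 to 85% at the fixed SE, and about 74 to 84% with that variance included.

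These figures rest on an assumed site effect and an assumed drift; the documents imply neither value. The remedy also rests on additivity. It does not address other differences between habitual lens wearers and habitual spectacle wearers.

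**What to change.** Add site as a fixed effect to the primary model in Protocol 12.4.1.2 and SAP 4.3.1. In the SAP code this is `class subject lens site;` and `model transitiontime = lens site;`, with the MF versus PAL contrast coefficients unchanged. Report MF minus PAL by site as a descriptive check, since about six PAL subjects per site will not support a formal comparison.

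The cost is one model term. At the planned balance there is no power loss. If a site effect exists, the term recovers power: with an assumed 0.5 s effect, the unadjusted analysis has 88.4% power at the planned split, against 94.5% adjusted. Under heavy drift the variance rises as shown in the working. Power stays above 80% with 24 completers per site, but not at PAL 12:0 and MF 6:30. The protocol should say that complete separation would leave the contrast not estimable.

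Optionally, clarify Protocol section 8 so that site totals may vary but each site enrols both cohorts at about the planned 3:1 MF:PAL ratio. Apply this at enrolment. A ratio among completers is hard to operate, because completion is known only later and an unsuccessful lens fit removes MF subjects only. One cohort may have to wait at a site, which could slow recruitment somewhat.
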